#### *Dynamic mechanical allodynia*

Allodynia is a positive sign identified by physicians in about 70% of CRPS patients and a self-reported symptom by almost 90% of the CRPS patients (Harden et al. 2010b). The DMA measurement is part of the Quantitative Sensory Testing protocol developed by the German Research Network on Neuropathic Pain as a comprehensive battery of sensory tests to quantify functions of the human somatosensory nervous system (Maier et al. 2010).

#### *Pressure pain threshold*

The PPT aims to quantify the mechanical deep somatic hyperalgesia in CRPS patients. Many patients with CRPS report pain in the depth of the limb rather than superficially in the skin, pointing

to the importance of deep somatic structures such as bones, joints, tendons, and muscles in the pathophysiology of CRPS (Mainka et al. 2014).

Pain localized in the deep tissues occurs frequently in CRPS. In addition, hyperalgesia to blunt pressure over muscles is common in CRPS. The PPT over the thenar muscle provides 77% sensitivity and 63% specificity in identifying a patient with CRPS (cutoff 293 kPa; Mainka et al. 2014).

#### *Edema measurement - figure-of-eight method*

Edema is a sign identified by physicians in about 65% of CRPS patients and a self-reported symptom by almost 90% of the CRPS patients (Harden et al. 2010b). Quantifications of edema are used to establish a baseline at the initial examination and to document changes in subject status. The figure-of-eight is a method of measuring edema by means of measuring tape and pre-defined anatomical landmarks. It demonstrated high intra-rater reliability, inter-rater reliability, and concurrent validity (Pellecchia 2003, Leard et al. 2004, dos Reis et al. 2004).

#### *Active range of motion - goniometry*

Decreased AROM is a sign identified by physicians in and a self-reported symptom by about 86% of CRPS patients (Harden et al. 2010b). The AROM is measured using an universal hand-held goniometer, based on the guidance recommended by the American Medical Association guidelines and by the American Society of Hand Therapists' clinical assessment recommendations. The AROM was applied for subjects with CRPS by Perez et al. 2003 and Oerlemans et al. 1998.

Possible threats to the reliability of the AROM measurements (more than one rater, [in]experience of the rater [unstructured] measurement protocols) have to be controlled for by using a rigid measurement protocol, valid and reliable measurement instruments, and, where possible, the same rater performing the initial and subsequent measurements for 1 subject (Perez et al. 2003).

#### *CRPS Severity Score*

The CRPS Severity Score has been shown to discriminate well between CRPS and non-CRPS patients and displayed strong associations with dichotomous CRPS diagnoses using both IASP diagnostic criteria and proposed revised criteria (Harden et al. 2010b). A higher CRPS Severity Score was associated with significantly higher clinical pain intensity, distress, and functional impairments, as well as greater bilateral temperature asymmetry and thermal perception abnormalities. Changes in the CRPS Severity Score show a strong correlation to changes seen in measures for depression and pain scores (Sayyad et al. 2011).

The following outcome measures selected for this trial were based on clinical outcome measures used in interventional trials in more common chronic pain conditions.

#### *Patient Global Impression of Change*

The 7-point PGIC is a subject-reported outcome measure tied to the conceptual framework of overall improvement. It is a recommended and responsive outcome domain for pain-related clinical trials (Dworkin et al. 2005, Farrar et al. 2001).

### *Patient Global Impression of Severity*

The PGI-S is a global index that may be used to rate the severity of a specific condition (a single-state scale). It is a simple, direct, easy-to-use scale that is intuitively understandable to clinicians (Yalcin et al. 2003).

### *EuroQol-5 dimension-5 level*

The EQ-5D-5L health questionnaire is a generic health-related quality of life instrument developed by a multidisciplinary team of European researchers. It provides a simple descriptive profile and a single index value that can be used in the clinical and economic evaluation of health care and in population health surveys to assess health outcome from a wide variety of interventions. The EQ-5D-5L is widely used in different countries by clinical researchers in a variety of therapeutic areas.

### *PROMIS-29 profile*

The PROMIS is an existing item bank of patient-reported outcome measures (Cella et al. 2007). It is a National Institute of Health (United States of America) funded system, which provides psychometrically sound and validated patient-reported outcome measures. These can be used in a wide range of chronic conditions. The PROMIS is comprised of calibrated item banks to measure diverse health concepts such as pain, physical function and depression presented for each domain as individual items and/or instruments of various lengths. In addition, PROMIS includes several collections of items, termed profiles, which measure multiple domains.

The PROMIS items can be compared directly with many standard instruments currently employed in clinical trials, such as the 36-item Short-Form Health Survey (SF-36) or Brief Pain Inventory (Choi et al. 2012).

The PROMIS-29 profile is recommended in COMPACT as a measurement tool for core outcome domains of depression, anxiety, physical function, pain interference, fatigue, sleep, and social participation, as well as an additional outcome measure for pain intensity (Grieve et al. 2017). For assessing the suicidal ideation, COMPACT recommends the supplementary use of the PROMIS-EDDEP39.

### *Short-Form McGill Pain Questionnaire 2: 6 neuropathic items*

The SF-MPQ-2 is a single measure of the major symptoms of both neuropathic and non-neuropathic pain. It has excellent reliability and validity, and the results of both exploratory and confirmatory factor analyses provided support for 4 readily interpretable subscales: continuous pain, intermittent pain, predominantly neuropathic pain, and affective descriptors (Dworkin et al. 2009).

The COMPACT consortium recommends the assessment of pain qualities using the 6 neuropathic items from the SF-MPQ-2 as these were considered to capture the essential qualities with minimum patient burden (Grieve et al. 2017).

### *Pain Catastrophizing Scale*

Trials in non-CRPS populations indicate catastrophizing is a prospective predictor of negative pain outcomes. The COMPACT consortium recommends the PCS be used to capture pain catastrophizing (Sullivan et al. 1995): a score of greater than 30 is thought to represent a problematic level of catastrophic thinking (Sullivan et al. 2009). Bean et al. (2016) reported the average PCS score at baseline was 22.0 in their sample of 66 patients diagnosed with CRPS within the previous 12 weeks, but underwent significant reduction to a mean score of 13.4 by 6 months as

treatment progressed ( $p<0.001$ ). This suggests pain catastrophizing as an important outcome and the PCS as a sensitive measurement tool.

#### *Pain Self Efficacy Questionnaire*

The PSEQ will be used to capture pain self-efficacy. The respondent considers how confident they are performing each activity, while taking their pain into account. This provides more clinically useful data than asking about performing an activity in isolation (Nicholas 2007). The accumulated evidence from a number of published trials and a confirmatory analysis with a large cohort of heterogeneous chronic pain patients attending a pain management program provide support for the original psychometric properties of the PSEQ developed with a sample of chronic low back pain patients (Nicholas 2007).

#### **Pharmacodynamic assessments**

##### *Bone turnover markers*

The bone biomarkers CTX (for resorption) and BAP and PINP (for bone formation) have been selected in accordance with recommendations for the selection of these particular biomarkers in other bone diseases, including osteoporosis (Wheater et al. 2013; Vasikaran et al. 2011). Disordered bone metabolism has been suspected in CRPS based on abnormalities observed on imaging (x-rays, bone densitometry and, in particular, bone scintigraphy using radiolabeled bisphosphonates). The selected markers are known to be responsive to and associated with the mechanism of action of bisphosphonates.

#### **Markers for disease severity or progression of CRPS**

##### *Soluble interleukin-2 receptor (sIL-2R)*

Interleukin-2 (IL-2) is a cytokine crucially important in regulating activation, proliferation, and survival of different T-cell subsets. This effect of IL-2 is mediated through the IL-2 receptor which consists of the common  $\gamma$ -chain (CD132), a  $\beta$ -chain (CD122), and an  $\alpha$ -chain (CD25). CD25 is strongly expressed on activated T-cells, which also secrete this molecule as a soluble variant (referred to as soluble IL-2 receptor; sIL-2R) from the cell membrane into the circulation.

According to Bharwani et al. 2017, plasma sIL-2R levels are significantly elevated in CRPS patients, indicating an increased T-cell activity in CRPS. This finding could point towards a T-cell-mediated inflammatory process in CRPS and sIL-2R could be a potential new marker to determine inflammatory disease activity in CRPS.

#### **Health economics outcome and work productivity data collection**

##### *Work Productivity and Activity Impairment Questionnaire: CRPS*

The WPAI questionnaire is a well validated instrument to measure impairments in work and activities. It has been validated to quantify work impairments for numerous diseases such as asthma, psoriasis, irritable bowel syndrome, ankylosing spondylitis, Crohn's disease, chronic non-malignant pain, low back pain, and neuropathic pain. In addition, the WPAI questionnaire has been used to compare work impairments between treatment groups in clinical trials or between subjects with different disease severity levels.

*Medical resource utilization and health economics data*

The data collected by means of this exploratory assessment will support determining the type and frequency of healthcare services used by CRPS patients. This information, correlated with corresponding costs, may be used in developing an evidence-based economic model.

## **12.10 Compliance**

Compliance is the adherence to all requirements of the trial protocol.

Trial site compliance will be assured by the implementation of a quality system and the performance of a combination of trial site visits, training, and monitoring visits. Non-compliance should lead to prompt action by the sponsor to secure compliance.

Compliance of the subjects to record their pain intensity assessments in the electronic diary will be checked by the investigator at the respective visits. A non-compliant subject may be withdrawn from the trial at the discretion of the investigator.

Relevant deviations from the protocol will be documented and described in the integrated clinical trial report.

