**Other data to be collected that are not directly attributed to or considered as an endpoint**

---

General note: All efficacy and safety data evaluated during Treatment Period B and Follow-up Period 2 will be analyzed descriptively separately for subjects who are treated in Treatment Period B and subjects who are not treated. For subjects treated in Treatment Period B, analyses will be performed for subjects initially treated with placebo and subjects initially treated with neridronic acid.

All efficacy assessments will be evaluated for the time points indicated in the schedules of events.

*To assess the efficacy of neridronic acid in subjects with CRPS*

- Change from baseline in average pain intensity recorded on the tablet computer.
- Change from Week 26 in average pain intensity recorded on the tablet computer.
- Pain response to treatment, defined as at least 50% decrease from baseline in the average pain intensity, based on pain intensity recordings on the tablet computer.
- Pain response to treatment, defined as at least 50% decrease from Week 26 in the average pain intensity, based on pain intensity recordings on the tablet computer.
- Pain response to treatment, defined as at least 30% decrease from baseline in the average pain intensity, based on pain intensity recordings on the tablet computer.
- Pain response to treatment, defined as at least 30% decrease from Week 26 in the average pain intensity, based on pain intensity recordings on the tablet computer.
- Change from baseline in pain intensity scores determined using worst and current pain ratings recorded daily in the electronic diary.
- Change from baseline in worst and current pain intensity ratings, recorded on the tablet computer.
- Change from Week 26 in worst and current pain intensity ratings, recorded on the tablet computer.
- Duration of effect based on average pain intensity recordings in the electronic diary.
- Change from baseline in the pain intensity level of DMA.
- Change from baseline in PPT ratios.
- Change from baseline in the ratio of the figure of eight measurements of the affected limb versus the unaffected limb.
- Change from baseline in the active range of motion (AROM) ratio (affected limb and unaffected limb) measured in the hand or foot, respectively.
- Change from baseline in the CRPS Severity Score.
- Patient Global Impression of Change (PGIC).
- Patient Global Impression of Severity (PGI-S).

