### **1.5.3.1 Primary endpoint**

See Section 1.2 for the definition of the primary endpoint.

For the primary objective of the trial, the primary estimand is the difference in means of the primary efficacy endpoint of 400 mg intravenous neridronic acid compared to placebo for all allocated and treated subjects. This treatment policy or *de facto* estimand measures the effect of neridronic acid regardless of adherence to treatment or protocol.

The primary estimand will be estimated by the analysis of the primary efficacy endpoint for the Full Analysis Set. The primary analysis will fit a mixed model for repeated measures (MMRM) to the change from baseline in the average pain intensity scores from Week 1 to Week 12 recorded once daily in the electronic diary, including the covariate baseline pain intensity score, and the factors geographic region, week, treatment, and treatment-by-week interaction as fixed effects, and an unstructured covariance matrix to model the covariance structure of the repeated measurements.

The primary efficacy analysis will be performed using the contrast, i.e., the mixed model Wald test, of neridronic acid 400 mg versus placebo at Week 12 of the treatment, week and treatment-by-week interaction term of the mixed effects model described above. Model-based parameter estimates, standard errors, 95% confidence intervals, and p-values will be tabulated. This analysis will be performed using only the observed values without imputation of missing values.

Additional sensitivity analyses will be performed to assess the robustness of primary analysis results. Sensitivity analyses will include the imputation of missing pain intensity scores using different pattern mixture models (PMMs).

A descriptive summary of the weekly averages and the changes from baseline will be generated by treatment group. Graphical displays will be used if appropriate.

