### **7 TRIAL OBJECTIVES AND ENDPOINTS**

The trial objectives and endpoints are given in Section [1.2](#).

The pain intensity score used for the primary endpoint will be calculated from average pain intensity ratings, assessed once daily in the electronic diary and referring to the CRPS-affected limb. The baseline average pain intensity score is defined as the average of the week before allocation to treatment at Visit 2 and calculated as the average of the 7 average pain intensity ratings starting in the evening of Day -7 until Day -1. A baseline pain intensity score ( $\geq 4$  on the NRS) must be confirmed at the site prior to subject allocation (at Visit 2). Subjects who do not meet eligibility criteria due to inadequate pain ( $< 4$  on the NRS) will be excluded from the trial.

Pain intensity scores from Week 1 through Week 12 will be calculated in a similar manner using average pain intensity ratings obtained from the electronic diary. The Week 12 pain intensity score, for evaluation of the primary outcome, will be the average of up to 7 possible ratings obtained in the 7-day period culminating with the rating obtained in the evening prior to the Week 12 visit.

Handling of missing pain ratings will be addressed in the statistical analysis plan. Compliance with the pain ratings in the electronic diary must be monitored and subjects with insufficient ratings ( $< 4$  ratings per week for 2 weeks) should receive a reminder and undergo re-training.

During Visit 2 (Day 1), Visit 7 (Week 6), Visit 8 (Week 12), Visit 9 (Week 16), and Visit 11 (Week 26), Visit 16 (Week 36), and Visit 17 (Week 52), the subjects will be asked to record the pain intensity ratings for average, worst, and current CRPS-related pain directly on a tablet computer maintained at the site. For subjects included in Treatment Period B, the subjects will also be asked to record pain intensity rating at Visit 12, Visit 13, Visit 14, and Visit 15. Worst and average pain intensity ratings will be based on a 24-hour recall period. The pain ratings and other patient-reported outcomes from the tablet computers recorded up to Week 26 as well as DMA, edema, and PPT assessment will be used for the secondary endpoints.

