## **9.3 Subject discontinuation from the trial or IMP**

Once a subject enrolls in this trial, whilst protecting subject safety, the trial site should make every effort to retain the subject for the planned duration of the trial.

A subject may withdraw consent at any time.

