### **9.3.1 Subject discontinuation from the trial**

All bisphosphonates have a long retention time in bone, and duration of efficacy is related to their persistent effects on bone turnover, specifically the inhibition of activation of bone resorption (Al Nofal et al. 2015; Naylor and Eastell 2012; Jung and Lein 2014). Collection of follow-up data is important for characterizing the safety and efficacy of neridronic acid. Subjects who receive any treatment, even a partial infusion, should be encouraged to remain in the trial for the full duration for follow-up safety and efficacy assessments.

Under certain situations, discontinuation from the trial may be required or be in the best interest of the subject from a risk/benefit perspective. [Table 1](#) lists mandatory and optional reasons for discontinuation from the trial.

Table 1: Reasons for compulsory and optional discontinuation of subjects

Reason	Discontinuation from trial	
	Compulsory	Optional
Enrollment failure (i.e., subject was not allocated to treatment due to failure to meet inclusion or exclusion criteria and did not receive IMP).	X	
Subject withdrawal of consent (the reason for withdrawal must be specified).	X	
Subject death.	X	
Subject loss to follow-up (i.e., no further contact with the subject is possible).	X	
Sponsor decision to discontinue the subject.	X	
Technical reasons (e.g., site is no longer able to function or participate in the trial, and the subject is too remote from other site locations).		X
Sponsor decision to terminate the trial.	X	
Other reasons (e.g., subject becomes engaged in litigation related to their disability from CRPS in which monetary gain may affect their objective participation in the trial).		X

CRPS = complex regional pain syndrome, IMP = investigational medicinal product.

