#### **11.1.3.4        Visit 9 (Day 113 [Week 16]; ±4 days)**

The following evaluations will be performed:

- Record vital signs.
- Record concomitant medications and therapies.
- Record adverse events.
- Complete the assessment of the signs and symptoms of CRPS (for details, see Section 12.3.6).
- Compliance assessment for electronic diary.
- Check trial discontinuation criteria.
- Ask the subject to record the average, worst, and current pain on the tablet computer at the site.
- Ask the subject to complete the pain intensity question (question number 29, GLOBAL07) of the PROMIS-29 profile.
- Ask the subject to complete the PGI-S.

- Ask the subject to complete the PGIC.

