#### **12.3.1.1 Electronic diary**

Subjects will be asked to record their average, worst, and current CRPS-related pain intensity once daily in the electronic diary (in the evening), using an 11-point NRS (from 0 = “no pain” to 10 = “pain as bad as you can imagine”) starting at Visit 1 and continuing until Visit 8. Worst and average pain intensity will be for a 24-hour recall period.

After Visit 8 up to Visit 17, subjects will be asked to record their average, worst, and current CRPS-related pain intensity once weekly in the electronic diary (in the evening) using the same 11-point NRS and a 24-hour recall period.

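### Section 12.10 lets an investigator end trial participation over poor diary recording, with no threshold or prior step, although no secondary endpoint comes from the diary

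*Protocol*

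**What the plan says.** Section 12.10 opens by defining compliance as keeping to the whole protocol. It then says that diary recording of pain will be checked at visits, and continues: "A non-compliant subject may be withdrawn from the trial at the discretion of the investigator". No threshold, warning step or time limit is attached.

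Other parts of the protocol point towards keeping subjects in:

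- Section 1.5.3.1 (repeated in 14.1.7.1.1): the primary estimand "measures the effect of neridronic acid regardless of adherence to treatment or protocol".
- Section 9.3: "the trial site should make every effort to retain the subject for the planned duration of the trial".
- Section 9.3.1: anyone who received even a partial infusion "should be encouraged to remain in the trial for the full duration for follow-up safety and efficacy assessments".
- Section 9.3.2 and Table 2: serious non-compliance with procedures is a reason to stop IMP. Subjects stopped from IMP should stay in the trial unless a Table 1 reason applies, and Table 1 has no row for non-compliance.
- Section 7: subjects with fewer than 4 diary ratings per week for 2 weeks "should receive a reminder and undergo re-training". This is the only numeric diary rule after allocation, and it does not lead to withdrawal.

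Until Visit 8 the diary is daily. From then to Visit 17 subjects record "current CRPS-related pain intensity once weekly in the electronic diary" (Section 12.3.1.1). Section 1.2 lists the use of these later entries as "Duration of effect based on average pain intensity recordings in the electronic diary", under data not considered an endpoint. The visit lists for Visits 9 to 17 still include the item "Compliance assessment for electronic diary".

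**The concern.** The sanction is wider than the thing it polices. The diary supplies the primary endpoint. It supplies no secondary endpoint, and after Week 12 no endpoint at all. Removing a subject from the trial for diary gaps also removes tablet ratings and site measurements that could still have been collected.

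The result would be missing data of the kind that Section 1.5.3.3 says the trial will try to limit. A discretionary withdrawal may be related to how the subject is doing. Subjects are not replaced (Section 9.3.3.3), and no SAP can recover an assessment that was never made.

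**Working it through.** **Sample size, for context.** Section 1.5.1 states 86 per arm for a difference of 1.0, SD 2.0, one-sided 2.5% and 90% power. The normal approximation gives n = 2 × (1.960 + 1.282)² × 2.0² / 1.0² ≈ 84.1, so 85. The noncentral t calculation gives 89.99% power at 85 and 90.3% at 86. The stated 86 is therefore reproduced, and this point does not challenge it. The step to 90 per arm (91.6% power) is explained only by the optional futility look; no allowance for lost subjects is stated.

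**Endpoints by data source (Section 1.2).**

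| Endpoint | Source | Time | Confirmatory (Section 1.5.3.4) |
|---|---|---|---|
| Primary: average pain | Diary | Week 12 | Yes |
| Average pain change | Tablet | Week 26 | Yes |
| 30% response | Tablet | Week 12 | No |
| 30% response | Tablet | Week 26 | No |
| DMA | Site test | Week 12 | Yes |
| PPT ratio | Site test | Week 12 | Yes |
| Edema ratio | Site measurement | Week 12 | Yes |

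Secondary endpoints from the diary: 0 of 6 (3 tablet, 3 site). Confirmatory set: 1 primary + 4 secondary = 5.

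**Endpoint values lost per subject, assuming no follow-up after withdrawal.**

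| Situation | Confirmatory lost | Secondary lost |
|---|---|---|
| Withdrawn before Visit 8 | up to 5 of 5 | up to 6 of 6 |
| Kept, no usable Week 12 diary data | 1 of 5 | 0 of 6 |
| Withdrawn between Visit 8 and Visit 11 | 1 of 5 | 2 of 6 |
| Kept over the same period, weekly entries missed | 0 of 5 | 0 of 6 |
| Withdrawn after Visit 11 | 0 of 5 | 0 of 6 |

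The counts are maxima because DMA, PPT and edema are analyzed only in subjects who meet a baseline condition (Section 1.5.3.2).

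**Length of the exposed period.** Visit 8 is Day 85, Visit 11 is Day 183 and Visit 17 is Day 365. From Visit 8 to Visit 11 is (183 − 85)/7 = 14 weeks, with diary checks at Visits 9 and 10 before the Week 26 assessment. The remaining (365 − 183)/7 = 26 weeks of the weekly phase cannot affect a listed endpoint.

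**The reminder trigger after Visit 8.** One average rating per week is requested, or 3 ratings if worst and current pain are counted. Both are below 4, so the Section 7 trigger cannot separate compliant from non-compliant subjects in the weekly phase. The protocol gives no other trigger.

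**Responder analysis.** Section 1.5.3.2 counts a missing tablet score as non-response. With 90 per arm, each would-be responder who is withdrawn lowers that arm's counted rate by 1/90 = 1.1 percentage points.

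**Power, as an illustration only.** The protocol gives no withdrawal rate. If withdrawn subjects contributed nothing, which is a worst case, 90 per arm would give 90.2% power at 5% withdrawn, 88.6% at 10% and 84.6% at 20%.

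**The case against.** The strongest reply is that nothing here is a contradiction. Section 12.10 says what the investigator may do. The retention texts say what sites should do, which Section 3.2 defines as recommended rather than mandatory. Table 1 has an open-ended optional row for other reasons that could cover this case. That reply stands: a reader might infer that Section 12.10 breaches Section 9.3 or Table 1, and the wording does not support it.

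Several limits on the consequences also stand:

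- Section 8.2 asks subjects who withdraw to continue follow-up visits if possible. It is written mainly about withdrawal by the subject, but it means that the losses above are not certain. The Early Termination Visit in Section 9.3.3.1 is likewise only done if possible, and it happens when the subject leaves, not at Week 12 or Week 26.
- MMRM is used for the primary endpoint and for the Week 26 tablet endpoint, with a similar model for DMA, PPT and edema. Earlier visits of a withdrawn subject still contribute. MNAR analyses are planned for the primary endpoint. Individual values are lost, not tests.
- Investigators are blinded. Bias is possible but not shown.
- The two responder endpoints lie outside the confirmatory set.
- The Section 7 trigger follows the text on the Week 1 to 12 scores. The protocol never says that it governs weekly entries, so its failure there is a gap, not an error in that rule.

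Finally, because Section 12.10 opens with compliance in general, its last sentence may be meant for any serious non-compliance, with diary checks as the preceding example. Deleting it outright could remove more than intended. That bears on the fix; it does not make the sentence better suited to diary gaps.

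**Conclusion.** The point holds as a tension worth removing. As written, an investigator can end participation over diary gaps without any criterion, which works against the estimand, the retention text, the Table 2 approach and the Section 7 reminder.

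Per subject, the avoidable loss before Visit 8 is up to 4 further confirmatory values (5 instead of 1). In the 14 weeks between Visit 8 and Visit 11 it is the Week 26 tablet value (1 instead of 0), which also becomes a counted non-response. These counts assume no follow-up after withdrawal and a subject who meets the baseline conditions for DMA, PPT and edema.

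The number of subjects affected is unknown, and no figure in the protocol is shown to be wrong. It would go too far to say that the primary result is biased, that confirmatory tests are lost, or that the diary has no use after Week 12: it still feeds a descriptive outcome. The change is worth making because the loss is avoidable at almost no cost.

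**What to change.** Reword Section 12.10 so that diary non-compliance alone is not a reason for withdrawal from the trial. It should lead to the reminder and re-training in Section 7, while all scheduled visits, tablet ratings and site measurements continue.

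Add a reminder trigger that works after Visit 8, for example two consecutive missed weekly entries. If discretion is wanted for serious general non-compliance, state it separately and reconcile it with Section 9.3 and Tables 1 and 2. The rules for stopping IMP and for entering Treatment Period B need no change for this point.

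The cost is wording in Sections 12.10 and 7. No procedure is added, since the visits and assessments are already scheduled. The small downside is less investigator discretion and some continued follow-up of subjects with poor diary data.
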